Study protocol:
Impact of Repeated Antioxidant
Supplementation of Embryo Culture Media on
Blastocyst Utilization and Expansion Rate Under
Two Different O₂
Concentrations

October 31st, 2021

Title: The Role of Antioxidants in Mitigating Reactive Oxygen Species and Oxidative Stress in Assisted Reproduction Techniques: A Comparative Study

Introduction:

During assisted reproduction techniques (ARTs), monitoring the laboratory environment is essential for adequate embryo development and any deviation from optimal conditions could increase reactive oxygen species (ROS) (Kaskar, 2021). Excessive ROS is detrimental to early embryo development (Kaskar, 2021). Reactive oxygen species constitute highly reactive chemicals associated with oxidative stress (OS) and subsequent cellular damage to gametes and embryos (Lane & Lyons, 2000; Swain, 2010). Oxidative stress is observed when the accumulation of ROS molecules exceeds the capacity of antioxidants (AOXs) defense mechanisms to neutralize them, subsequently promoting lipid, protein, as well as DNA damage (Lane & Lyons, 2000; Swain, 2010).

In the past, embryo culture was performed in atmospheric O₂ concentrations of about 20% (Nastri et al., 2016). However, an O₂ concentration of 5% was found superior in terms of enhancing clinical pregnancy rate, live births, as well as implantation rate (Kaskar, 2021). Several exogenous factors affecting embryo development during in vitro culture, namely the type of infertility, as well as advanced maternal and paternal age, have been correlated with high levels of ROS production in gametes and embryos, which in turn result in decreased fertilization, implantation, and live birth rates, and increasing aneuploidy rates (Lane & Lyons, 2000; Edwards et al., 1998; Hong et al., 2014; Chui et al., 2008)

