- Group 1A: Antioxidants will be administered every 12 hours at 5% O₂ tension.
- Group 1B: Antioxidants will be administered every 12 hours at 20% O₂ tension.
- Group 2A: Antioxidants will be administered once at the beginning of embryo culture at 5% O₂ tension.
- Group 2B: Antioxidants will be administered once at the beginning of embryo culture at 5% O₂ tension.

Methods:

Study Location and Duration:

The study will be conducted at the Center for Technological Innovation and Reproductive Medicine (CITMER), Mexico City, Mexico, from October 2021 to May 2022.

Participants:

Eligible participants will include infertile women with tubal factor, polycystic ovary syndrome, uterine factor, and unexplained infertility, who have had fertilization of more than 2 oocytes by conventional in vitro fertilization (cIVF) and intracytoplasmic sperm injection (ICSI).

Exclusion criteria will involve low ovarian response patients (fewer than 6 oocytes obtained after oocyte retrieval) and patients older than 37 years.

Sample Size and Group Allocation:

A total of 3603 zygotes obtained from 293 patients will be included in the study.

The zygotes will be divided into four groups based on the following conditions:

Group 1A: Antioxidants will be administered every 12 hours at 20% O₂ tension (793 zygotes).

Group 1B: Antioxidants will be administered only at the beginning of embryo culture at 20% O₂ tension (1286 zygotes).

Group 2A: Antioxidants will be administered every 12 hours at 5% O₂ tension (695 zygotes).

Group 2B: Antioxidants will be administered only at the beginning of embryo culture at (829 zygotes).

The procedures followed for IVF/ICSI involved the following steps:**Ovarian stimulation:**

Different ovarian stimulation protocols were used, including the gonadotropin-releasing hormone (GnRH) antagonist protocol with Cetrotide®, in combination with rFSH and rLH in Pergoveris®.

GnRH antagonist protocols were also used with follitropin alfa in Gonal-F® or with human menopausal gonadotropin in Merapur®

Gamete Retrieval:

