Statistical analysis plan:

Impact of Repeated Antioxidant Supplementation of Embryo Culture Media on Blastocyst Utilization and Expansion Rate Under Two Different O₂ Concentrations

October 31st, 2021

Research Questions:

- What is the effect of antioxidant supplementation and O2 tension on blastocyst utilization rate and blastocyst expansion rate in infertile women?
- Are there any significant differences in the outcomes between the different antioxidant supplementation protocols and O2 tensions?

Statistical Tests:**Sample Size:**

The total number of blastocysts analyzed was 1797, obtained from 3603 zygotes and 4924 inseminated oocytes. The study included 293 infertile women with a mean age of 32.2 ± 3.3 years.

Data Handling:

For statistical analysis, the data collected consisted of the continuous variable of age, which was expressed as the mean \pm standard deviation in each study group. In addition, the frequency and percentage of usable and expanded blastocysts were recorded as categorical variables.

Comparisons between treatments were performed by calculating the odds ratio and the chi-square test. A significance level of $p < 0.05$ was established to determine the existence of statistically significant differences between groups.

Confounding Variables:

Other treatments or medications: Although there is no explicit mention of other treatments or medications received by the participants in addition to antioxidant supplementation, it is essential to acknowledge that there may be confounding variables present. It is possible that other interventions or medications used in the management of infertility could interact with antioxidant supplementation and potentially influence the study outcomes.

Sensitivity analysis:

The odds ratio analysis with a confidence interval of 95%

9. Statistical Software:

R Core Team was employed for statistical analysis.

10. Data Interpretation:

The results were interpreted by analyzing and comparing the blastocyst utilization rates, blastocyst expansion rates, and cumulative blastocyst utilization and expansion rates across the four study

groups. Statistical analyses, such as odds ratios (OR) and chi-square tests, were used to determine the significance of the differences observed. The level of significance was set at $p < 0.05$.

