The findings indicated that antioxidant supplementation had a positive impact on the development and usability of blastocysts. The groups receiving antioxidant supplementation every 12 hours (groups 1A and 2A) consistently showed higher blastocyst utilization and expansion rates compared to the groups with antioxidant supplementation only at the beginning of embryo culture (groups 1B and 2B). These results suggest that regular and sustained antioxidant exposure during embryo development may enhance the overall quality and viability of blastocysts.

Additionally, subgroup analyses were conducted based on the O₂ tension (20% vs. 5%) and the timing of antioxidant supplementation (every 12 hours vs. baseline only). These subgroup analyses allowed for a more detailed understanding of the effects of different conditions on blastocyst outcomes. The subgroup analyses consistently demonstrated that the groups with regular antioxidant supplementation every 12 hours (groups 1A and 2A) had superior blastocyst utilization and expansion rates compared to the groups with baseline-only supplementation (groups 1B and 2B).

In terms of clinical or practical significance, the findings suggest that incorporating antioxidant supplementation, particularly with a frequent administration schedule, can improve the development, expansion, and overall utilization of blastocysts in assisted reproductive technologies. This may have important implications for infertility treatments, as higher blastocyst quality and viability are associated with increased chances of successful embryo transfer and higher pregnancy rates. By optimizing embryo culture conditions through antioxidant supplementation, clinicians and embryologists can potentially improve clinical outcomes and increase the success rates of infertility treatments, offering hope to couples struggling with fertility issues.

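### The SAP does not specify that the supplementation-schedule comparison is made within O₂ level, although the O₂ mix differs between the two schedules

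*SAP*

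**What the plan says.** **Method.** The SAP (Data Handling) names one approach: "Comparisons between treatments were performed by calculating the odds ratio and the chi-square test". The protocol (Statistical Methods) names the same two tools. The SAP's Confounding Variables paragraph discusses other treatments and medications and does not mention O₂. Its sensitivity analysis is an odds ratio with a 95% interval. No stratified estimator, model term or interaction is named.

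**Conclusion drawn.** SAP section 10 says that 1A and 2A did better "compared to the groups with antioxidant supplementation only at the beginning of embryo culture (groups 1B and 2B"). It also says that rates were compared across the four groups and that subgroup analyses by O₂ tension and by timing were carried out. The subgroup result is again worded as 1A and 2A against 1B and 2B, with no separate result for each O₂ level.

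**Group sizes** (protocol, Sample Size and Group Allocation):

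- There are 793 zygotes in 1A, the 12-hourly group at the higher O₂ setting.
- The once-only group at that same setting is the largest of the four: "Group 1B: Antioxidants will be administered only at the beginning of embryo culture at 20% O₂ tension (1286 zygotes").
- There are 695 zygotes in 2A, the 12-hourly group at the lower O₂ setting.
- The remaining once-only group has a line in which the O₂ level is absent: "Group 2B: Antioxidants will be administered only at the beginning of embryo culture at (829 zygotes").

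**O₂ effect.** The protocol's Introduction says that "an O₂ concentration of 5% was found superior", with reference to clinical pregnancy, live birth and implantation. It does not mention blastocyst rates.

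**The concern.** Schedule and O₂ setting form a 2×2 layout with unequal cells. If the two schedules have different shares of zygotes at each O₂ setting, a crude comparison of all 12-hourly with all once-only zygotes estimates the schedule effect plus a fraction of the O₂ effect. The test then no longer has its nominal error rate when the schedule has no effect.

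The conclusion at stake is the trial's main one, that repeated supplementation is better. The O₂ setting is a design factor known for every zygote, so there is no practical reason to leave it out of the estimator. The SAP's first research question asks about both supplementation and O₂ tension, so the reader needs to know how the two are separated.

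**Working it through.** **Inputs.** The group sizes are those above. The schedule labels (1A and 2A 12-hourly, 1B and 2B once only) agree between this list, the protocol's Antioxidant Supplementation section and SAP section 10. Group 2B is taken as 5% O₂ because that is the only empty cell.

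**Reproducing the plan's total.** 793 + 1286 + 695 + 829 = 3603, which matches "A total of 3603 zygotes obtained from 293 patients will be included in the study".

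**O₂ mix by schedule.**

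- 12-hourly: 793 + 695 = 1488 zygotes. At 20% O₂: 793/1488 = 53.3%. At 5% O₂: 695/1488 = 46.7%.
- Once only: 1286 + 829 = 2115 zygotes. At 20% O₂: 1286/2115 = 60.8%. At 5% O₂: 829/2115 = 39.2%.
- Difference in the 5% O₂ share: 0.4671 − 0.3920 = 0.0751.

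**Bias of a pooled crude difference when the schedule has no effect.** Bias = 0.0751 × D, where D is the blastocyst rate at 5% O₂ minus the rate at 20% O₂. The documents do not give D, so a range is assumed in both directions.

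**Standard error of the pooled difference.** With a rate near 50% (1797 blastocysts from 3603 zygotes is 49.9%) and independent zygotes, SE = √[0.25 × (1/1488 + 1/2115)] = 1.69 points. The type I error is the probability that a normal statistic shifted by bias/SE falls beyond ±1.96.

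| Assumed D (points) | Bias (points) | Bias/SE | Two-sided type I error |
|---|---|---|---|
| 0 | 0 | 0 | 5.0% |
| ±5 | ±0.38 | ±0.22 | 5.6% |
| ±10 | ±0.75 | ±0.44 | 7.3% |
| ±15 | ±1.13 | ±0.67 | 10.2% |

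**On the odds ratio scale.** With a 45% rate at 20% O₂ and no schedule effect, the crude odds ratio is 1.015, 1.031 or 1.046 for D = 5, 10 or 15. For D = −10 it is 0.969. With a true within-stratum odds ratio of 1.30, the crude value is 1.336 for D = 10 and 1.257 for D = −10. On the same expected counts, the Mantel-Haenszel odds ratio over the two O₂ strata returns 1.000 and 1.300.

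**Scale of the problem.** The pooled comparison has 80% power for a difference of about (1.96 + 0.84) × 1.69 = 4.7 points. For the bias alone to reach z = 1.96, D would have to be about 1.96 × 1.69/0.0751 = 44 points.

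**Mirror contrast.** Of zygotes at 5% O₂, 695/1524 = 45.6% are 12-hourly. Of those at 20% O₂, 793/2079 = 38.1% are. A crude O₂ comparison would likewise absorb 0.075 of any schedule effect.

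**The case against.** **Pooling is not stated.** No section prescribes a single pooled 2×2 table. The SAP speaks of four groups and of subgroup analyses by O₂ tension, and the protocol's aim is assessed at two O₂ concentrations. The headline sentence can fairly be read as 1A v 1B and 2A v 2B. If those were the tests, this bias is zero. A reader might infer that the analysis ignored O₂, but the documents do not establish that. What stands is that the text leaves the matter open and names no within-O₂ estimate.

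**The direction is not known.** A reader might infer from the Introduction that any bias must favour the 12-hourly groups. The statement there concerns pregnancy, live birth and implantation, whereas the outcomes here are usable and expanded blastocysts. With no O₂ effect on these outcomes there is no bias, and if 5% O₂ is worse the tilt reverses.

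**The size is small and the error rates are rough.** The bias could not by itself create a large difference. The type I figures treat zygotes as independent, although they come from 293 women. As an illustration, assume an intraclass correlation of 0.1 and allocation of whole patients. With 3603/293 = 12.3 zygotes per woman, the design effect is about 1 + 11.3 × 0.1 = 2.1. With the standard error widened to match, the 10-point shift falls from 0.44 to about 0.30 standard errors and the type I error from 7.3% to about 6.1%. Clustering is a separate and larger matter.

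**The inputs are uncertain.** The list under Allocation (Research Design) makes 1B 12-hourly and puts both 2A and 2B at once only with 5% O₂. It conflicts with the list used here, and the two must be reconciled. The denominator of the rates is also not defined. If it is blastocysts rather than zygotes, the O₂ mix cannot be computed.

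**Conclusion.** The point holds as a gap in specification. The SAP words its main and subgroup conclusions as 1A and 2A against 1B and 2B, names only a crude odds ratio and chi-square test, and does not say that the schedule is compared within O₂ level. On the list with counts, the O₂ mix differs by 7.5 percentage points between schedules, so a pooled crude analysis would be biased by 0.075 times the O₂ effect on blastocyst rates.

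For O₂ effects of up to 15 points in either direction, the bias is at most about 1.1 points and the type I error at most about 10%. This rests on four assumptions: 2B is at 5% O₂, zygotes are the denominator, zygotes are independent, and the comparison is in fact pooled. The documents support neither the claim that O₂ was left out of the analysis nor the claim that the result is tilted towards 12-hourly supplementation. The change is worth making because the factor is known for every zygote and adjusting for it is nearly free. It does not by itself overturn the reported conclusion.

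**What to change.** State in the SAP that the schedule effect is estimated within O₂ level:

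- Report 1A v 1B and 2A v 2B separately, with odds ratios and 95% intervals.
- Make any overall schedule estimate either a Mantel-Haenszel odds ratio over the two O₂ strata or an estimate from a logistic model with schedule, O₂ setting and their interaction. If the interaction is in the model, say how the two within-O₂ effects are averaged.
- Use patient-clustered standard errors. The usual Mantel-Haenszel variance does not allow for clustering.
- Stratify the O₂ contrast by schedule in the same way.
- Do not base the schedule conclusion on pooled crude percentages.
- Describe the O₂ contrast as one of incubator settings, because the protocol (Embryo Culture) gives 95% relative humidity with 20% O₂ and 25% with 5% O₂.
- Reconcile the protocol's two group lists, complete the 2B line, and state the denominator of each rate.

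The cost is a line of SAP text and the matching R code. No new data are needed. If within-O₂ analyses were already done, the sponsor need only say so and report them.

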Timeline and Frequency of Assessments:

Data collection will be performed at specific time points, specifically on day 5 and day 6 of the study.

Outcome Measures:

- Usable blastocysts on day 5.
- Expanded blastocysts on day 5.
- Usable blastocysts on day 6.
- Expanded blastocysts on day 6.
- Cumulative usable blastocysts.
- Cumulative expanded blastocysts.

Ethical Considerations:

The study was conducted in accordance with the Declaration of Helsinki and approved by the Institutional Ethics Committee of CITMER CE-20-102.

Data analysis

The statistical analysis of the data will be performed using the R statistical software by the R Core Team.

Statistical Methods:

For statistical analysis, the data collected consisted of the continuous variable of age, which was expressed as the mean \pm standard deviation in each study group. In addition, the frequency and percentage of usable and expanded blastocysts were recorded as categorical variables.

Comparisons between usable and expanded blastocysts from each treatment were performed by calculating the odds ratio and chi-square test. A significance level of $p < 0.05$ was established to determine the existence of statistically significant differences between groups.

References.

1. Khalied Kaskar, C. Optimizing embryo culture conditions and spent culture media analysis as predictors of embryo quality and pregnancy; PhD Thesis, University of the West Cape, Cape Town, South Africa, February 2021.
2. Swain, J.E. Optimizing the culture Environment in the IVF Laboratory: Impact of PH and Buffer Capacity on Gamete and Embryo Quality. *Reprod Biomed Online* **2010**, *21*, 6–16.
4. Nastri, C.O.; Nóbrega, B.N.; Teixeira, D.M.; Amorim, J.; Diniz, L.M.M.; Barbosa, M.W.P.; Giorgi, V.S.I.; Pileggi, V.N.; Martins, W.P. Low versus Atmospheric Oxygen Tension for Embryo Culture in

Assisted Reproduction: A Systematic Review and Meta-Analysis. *Fertil Steril* **2016**, *106*, 95-104.e17, doi:10.1016/j.fertnstert.2016.02.037.

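### The schedule-by-O2 layout is analysed only by odds ratios, chi-square tests and subgroup comparisons, so no planned estimate says how far the effect of 12-hourly supplementation differs by O2 level

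*SAP*

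**What the plan says.** The protocol's Introduction sets the aim: to learn whether 12-hourly supplementation improves usable and expanded blastocyst rates, assessed at 5% and at 20% O2. Both documents name the two O2 concentrations in their title. The SAP's second research question asks: "Are there any significant differences in the outcomes between the different antioxidant supplementation protocols and O2 tensions".

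The methods are brief. Protocol, Statistical Methods: "Comparisons between usable and expanded blastocysts from each treatment were performed by calculating the odds ratio and chi-square test". SAP, Data Handling: "Comparisons between treatments were performed by calculating the odds ratio and the chi-square test". The SAP's Sensitivity analysis adds a 95% confidence interval for the odds ratio, and significance is set at 0.05.

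SAP section 10 (Data Interpretation) then says that "subgroup analyses were conducted based on the O₂ tension (20% vs. 5%) and the timing of antioxidant supplementation", and concludes: "The subgroup analyses consistently demonstrated that the groups with regular antioxidant supplementation every 12 hours (groups 1A and 2A) had superior blastocyst utilization". The same is said of expansion, with the once-only groups as the comparator.

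Neither document contains an interaction term, a regression model, a homogeneity test or a ratio of odds ratios. The only mention of interaction, under Confounding Variables in the SAP, concerns other medications.

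**The concern.** The aim, the title and the second research question all bring in both factors, so a reader will want to know whether the benefit of the 12-hourly schedule depends on the O2 level. Section 10 ends with a general message for practice that is not limited to either O2 level, which makes the question a practical one.

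Separate odds ratios answer a narrower question: which way the effect points within each O2 level. If one subgroup is significant and the other is not, the true effects may still be identical. If both are significant in the same direction, the effects may still differ considerably. The quantity that addresses the question is the ratio of the two schedule odds ratios with its confidence interval, and no analysis in the plan produces it.

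**Working it through.** **Inputs from the documents.** Zygotes per group come from the second group list in the protocol (Sample Size and Group Allocation): 793 (12-hourly, 20% O2), 1286 (once, 20% O2), 695 (12-hourly, 5% O2) and 829 (once; the O2 level is missing from that line and 5% is inferred). Check: 793 + 1286 + 695 + 829 = 3603, the stated total. There is no power calculation to reproduce.

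**Assumptions.** The event rate is 50%. Rates by group are not given; 1797/3603 = 49.9% is blastocysts per zygote and serves only as a prompt. The test is two-sided at 0.05, zygotes are independent, and the subgroup at 20% O2 is independent of the one at 5% O2.

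**Standard errors.** At a 50% rate, Var(log OR) = 4(1/n₁ + 1/n₂).
- 20% O2: √[4(1/793 + 1/1286)] = 0.0903
- 5% O2: √[4(1/695 + 1/829)] = 0.1029
- Log ratio of ORs: √(0.0903² + 0.1029²) = 0.1369
- Pooled schedule effect: 1/√(1/0.0903² + 1/0.1029²) = 0.0679, so the interaction SE is 0.1369/0.0679 = 2.02 times as large.

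**Discordant subgroups when the true OR is the same.** Power in each subgroup is about Φ(ln OR/SE − 1.96). With powers a and b, P(exactly one significant) = a(1 − b) + b(1 − a). At OR 1.25, ln OR = 0.2231, a = 0.695 and b = 0.583, giving 0.695 × 0.417 + 0.583 × 0.305 = 0.468.

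| True OR at both levels | Power, 20% O2 | Power, 5% O2 | Exactly one significant |
|---|---|---|---|
| 1.20 | 0.524 | 0.426 | 0.50 |
| 1.25 | 0.695 | 0.583 | 0.47 |
| 1.30 | 0.828 | 0.723 | 0.35 |
| 1.40 | 0.961 | 0.905 | 0.13 |

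**What an interaction test could detect.** For 80% power the ratio of ORs must be at least exp(2.80 × 0.1369) = 1.47. The pooled schedule effect needs only OR exp(2.80 × 0.0679) = 1.21. With a design effect of 2 the interaction SE is 0.1369 × √2 = 0.1936 and the ratio is 1.72. Over event rates of 0.30 to 0.60 and design effects of 1 to 3, the detectable ratio runs from about 1.47 to 2.06.

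**Denominator.** The protocol (Variables to be Measured) defines expansion as a proportion of blastocysts. With about 1797 blastocysts split across groups roughly as the zygotes are, the SE grows by √(3603/1797) = 1.42 and the detectable ratio is again about 1.72.

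**The opposite error.** If the true OR is 1.0 at one level and 1.3 at the other, ln 1.3/0.1369 = 1.92. The interaction test then has about 48% power (27% with a design effect of 2), so even a formal test could easily miss such a difference.

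**The case against.** Several points on the other side are sound.

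- **Conduct.** A reader might infer that the plan sets one subgroup's p-value against the other's. The documents do not say so. Section 10 names no test for the subgroup analyses and claims no O2-dependent effect. Misreading a discordant pair is a risk that the method leaves open, not something the text reports.
- **Meaning of consistency.** Section 10 can be read as agreement in direction only. That statement needs no interaction test.
- **Objective.** Effect modification is not a named objective. Effects within each O2 level answer the literal aim. The question is implied by the aim and title, and by the unrestricted practice message.
- **Capability.** It is tempting to say that the trial cannot answer the question. It can: the four-group data support the test, and two odds ratios with intervals, one per O2 level, would allow an approximate ratio. What is missing is a specified contrast.
- **Illustration.** The 47% belongs to one assumed OR and lies near the maximum of about 50%. At OR 1.40 the figure is 13%.
- **Yield.** The interaction test is weak at these sizes and may well be inconclusive.

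These points limit the claim but do not remove the gap. Low power is a reason to report the ratio with its interval, since a wide interval shows how little the data say about dependence on O2.

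**Conclusion.** The point holds in a limited form. The plan provides for the direction of the schedule effect within each O2 level, but for no estimate of how far that effect differs between levels. Any statement that the effect is similar or different by O2 would therefore rest on nothing specified. This should be corrected, but it does not invalidate the within-level comparisons.

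The power figures are illustrative. They rest on an assumed event rate, on zygote denominators unless stated, and on independence. The protocol does not say how one woman's zygotes are spread over the groups. Design effects of 1 to 3 are assumed, and a split of siblings across groups could change the variance in either direction.

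Two further limits apply. The crossed layout itself rests on the second group list and on the Antioxidant Supplementation section; the list under Allocation labels the groups differently and places both 2A and 2B at 5% O2. Also, the protocol's Embryo Culture section pairs 20% O2 with 95% relative humidity and 5% O2 with 25%, so a reader who took an interaction as an effect of O2 alone would go too far. It is an interaction with incubator condition.

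**What to change.** 1. Reconcile the two group lists in the protocol, including the missing O2 level for 2B, before any contrast is coded.
2. For each outcome, fit one logistic model with schedule, O2 and schedule × O2, using standard errors clustered on the woman. State the denominator (zygotes or blastocysts) per outcome.
3. Report the schedule odds ratio at each O2 level and the ratio of the two with its 95% confidence interval. Base any statement that the effect differs or is similar by O2 on that ratio.
4. State that a non-significant interaction does not prove equal effects, and that humidity differs along with O2.
5. Label the analysis post hoc if results are already known; section 10 of the SAP already reports findings.

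The cost is a few lines of SAP text and R code, with no new data. The interval will be wide: under the independence assumption the 95% limits are the estimate divided and multiplied by exp(1.96 × 0.1369) = 1.31, or by exp(1.96 × 0.1936) = 1.46 with a design effect of 2.
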